1. REPORTING & ANALYSIS PLAN SYNOPSIS

Overview	Key Elements of the RAP
Purpose	
 This RAP details all planned analyses and outputs required for the final Clinical Study Report (CSR) of study 204824.
Protocol	
 This RAP is based on the protocol (Dated: 03-FEB-2016 for study 204824 [GlaxoSmithKline Document Number: 2015N240632_01]).
Primary Objective	
 Evaluate the efficacy of single intravenous dose administrations of GSK1070806 in prevention of delayed graft function (DGF) after transplantation.
Primary Endpoint	
 Proportion of subjects requiring dialysis during the first 7 days post transplant (excluding requirement for dialysis due to hyperkalemia within first 24 post-operative hours).
Study Design	
 Pilot, multicenter, single arm Bayesian sequential design study to evaluate the efficacy, safety, tolerability and pharmacokinetics (PK) of GSK1070806 in patients undergoing renal transplantation. Sample size (maximum of 30) had been selected to yield the probability of a “go” decision of 0.139 when the GSK1070806 DGF rate is 50% and 0.69 at what has been considered to be a clinically impactful GSK1070806 DGF rate of 35%.
Planned Analyses	
 Interim analyses are detailed within Section 3.1 where applicable. All decisions regarding final analysis, as defined in this RAP document, will be made prior to Database Freeze of the study data.
Primary Analysis Population	
 The ‘Analysis Population’ will be used to evaluate DGF related endpoints The ‘All Subjects Population’ will be used to evaluate study population; safety; PD/Biomarkers and other efficacy endpoints. The ‘PK’ population will be used to evaluate pharmacokinetics. The ‘Per-Protocol’ population will be used to evaluate the DGF rate in addition to the ‘Analysis Population’.
Hypothesis	
 The study is to determine the effect of GSK1070806 on DGF. Stopping rules have been defined to test whether the DGF rate is less than or equal to the null hypothesis rate of 50%.
Primary Analyses	
 A summary of the observed DGF rate during the study will be provided. The posterior probability that the proportion of subjects experiencing DGF is less than 50% will be calculated.
Secondary Analyses	
 Summaries of baseline and post-dose values or proportions of subjects at various time points will be provided. Graft survival will be summarized by Kaplan-Meier plots.

2. SUMMARY OF KEY PROTOCOL INFORMATION

2.1. Changes to the Protocol Defined Statistical Analysis Plan

Not applicable.

2.2. Study Objective(s) and Endpoint(s)

Objectives	Endpoints
Primary	Primary

 To assess the frequency of delayed graft function (DGF) in donation after circulatory death (DCD) renal transplant recipients treated with GSK1070806. 	
 Proportion of subjects requiring dialysis during the first 7 days post transplant, (excluding requirement for dialysis due to hyperkalemia within first 24 post-operative hours).
Secondary	Secondary

 To assess graft function in DCD renal transplant recipients treated with GSK1070806. 	
 Serum creatinine at baseline and over time post transplant. Urine output at baseline and over time post transplant. Proportion of subjects in the first 7 days with: 
 Primary Non Function Functional DGF Intermediate Graft Function Immediate Graft Function

 To assess the effect of GSK1070806 on acute rejection risk, and rejection/PD biomarkers. 	
 Proportion of subjects with episodes of biopsy-proven acute rejection. Rejection biomarkers/ PD markers (including serum IP-10 and Mig) at baseline and over time post transplant.

 To assess the effect of GSK1070806 on dialysis dependency and graft survival. 	
 Number of dialysis events per patient in the first 30 days post transplant. Proportion of subjects who are dialysis-independent at visits up to 12 months post transplant.

 To assess the safety and tolerability of GSK1070806 in renal transplant recipients. 	
 AEs and SAEs 
 Clinical laboratory values Vital signs Frequency, type and severity of infections

 To assess the pharmacokinetics of GSK1070806 in renal transplant recipients. 	
 Serum concentrations of GSK1070806 over time, and derived pharmacokinetic parameters if feasible (AUC, Cmax).

Objectives	Endpoints

 To assess the effect of GSK1070806 administration on serum IL-18 levels. 	
 Free, total, and GSK1070806 bound IL-18 at baseline and over time post transplant.

 To determine immunogenicity of GSK1070806 in renal transplant recipients. 	
 Frequency of anti-drug antibodies (ADAs) before and after GSK1070806 administration. ADA titers.

Objectives	Endpoints
Exploratory	Exploratory

 To assess the impact of GSK1070806 on urine biomarkers of renal injury. 	
 Serial measurements of urinary biomarkers, including KIM-1, NGAL and IL-18, at baseline and over time post transplant.

 To assess IL-18 target engagement in the kidney. 	
 GSK1070806 and IL-18 levels within renal graft biopsies, as assessed by immunohistochemistry.

 To assess the relation between IL-18 levels in renal preservation fluid and graft function. 	
 Level of IL-18 in renal preservation fluid.

 To assess the impact of GSK1070806 administration on IL-18 binding protein levels. 	
 Serum IL-18 binding protein at baseline and over time post transplant.

 To assess the humoral and cellular response to the transplanted organ in the presence of GSK1070806. 	
 Serum cytokine levels at baseline and over time post transplant. Histological analysis of biopsies with respect to cellular infiltrate.

 To assess health outcomes in renal transplant recipients following GSK1070806 administration. 	
 Length of hospital stay Re-hospitalization

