11.4.1.2. Derivations and Handling of Missing Baseline Data

Definition	Reporting Details
Change from Baseline	= Post-Baseline Visit Value – Baseline
[% Change from Baseline]	= [(Post-Baseline Visit Value – Baseline) / Baseline] x 100]

NOTE :

- Unless otherwise specified, the baseline definitions specified in [11.4.1.1Baseline Definitions](#) will be used for derivations for endpoints / parameters and indicated on summaries and listings.
- Unless otherwise stated, if baseline data is missing no derivation will be performed and will be set to missing.
- The baseline definition will be footnoted on all change from baseline displays.

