2.19	All Subjects	Non-Standard EFF_T1	Summary Statistics of Total IL-18		IA2, SAC
2.20	All Subjects	Non-Standard EFF_T2	Summary Statistics of total IL-18 Change from Baseline		IA2, SAC
Urine biomarker					
2.21	All Subjects	Non-Standard EFF_T1	Summary Statistics of IL-18		IA2, SAC
2.22	All Subjects	Non-Standard EFF_T1	Summary Statistics of NGAL		IA2, SAC
2.23	All Subjects	Non-Standard EFF_T1	Summary Statistics of KIM1		IA2, SAC

Efficacy Tables					
No.	Population	IDSL / TST ID / Example Shell	Title	Programming Notes	Deliverable
Dialysis dependency and graft survival					
2.24	All Subjects	Non-Standard EFF_T3	Proportion of Subjects Who are Dialysis-Independent at Visits up to 12 Months post Transplant		IA2, SAC
Exploratory					
2.25	All Subjects	Non-Standard EFF_T2	Summary Statistics of % Free GSK1070806 within Renal Graft Biopsies		IA2, SAC
2.26	All Subjects	Non-Standard EFF_T2	Summary Statistics of % Bound GSK1070806 within Renal Graft Biopsies		IA2, SAC
2.27	All Subjects	Non-Standard EFF_T2	Summary Statistics of Level of IL-18 in Renal Preservation Fluid		IA2, SAC
2.28	All Subjects	Non-Standard EFF_T2	Summary Statistics of Serum Cytokine Levels		IA2, SAC
2.29	All Subjects	Non-Standard EFF_T1	Summary Statistics of Length of Hospital Stay		IA2, SAC

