11.9.11. Non-ICH Listings

Non-ICH Listings					
No.	Population	IDSL / TST ID / Example Shell	Title	Programming Notes	Deliverable
PK					
20	PK	PKCL1P	Listing of Plasma GSK1070806 Pharmacokinetic Concentration-Time Data		IA2, SAC
21	PK	PKPL1P	Listing of Derived Plasma GSK1070806 Pharmacokinetic Parameters	Include dose and dose number	IA2, SAC
Graft Function					
22	Analysis Population	Non-Standard SAFE_L1	Listing of Individual Serum Creatinine		IA1, IA2, SAC
23	Analysis Population	Non-Standard SAFE_L1	Listing of Individual AUC of 7 Day Serum Creatinine	No change from baseline column	IA1, IA2, SAC
24	Analysis Population	Non-Standard SAFE_L1	Listing of Individual AUC of 30 Day Serum Creatinine	No change from baseline column	IA1, IA2, SAC
25	All Subjects	Non-Standard SAFE_L2	Listing of Individual Graft Function in the First 7 Days	Including primary non function;3 day functional DGF; 7 day functional DGF; 3 day intermediate graft function; 7 day intermediate graft function; 3 day immediate graft function; 7 day immediate graft function	IA1, IA2, SAC

Non-ICH Listings					
No.	Population	IDSL / TST ID / Example Shell	Title	Programming Notes	Deliverable
26	All Subjects	Non-Standard SAFE_L2	Listing of Individual Urine Output	Including change from baseline	IA2, SAC
27	All Subjects	Non-Standard SAFE_L1	Listing of Individual with Episodes of Biopsy-Proven Acute Rejection		IA2, SAC
Pharmacodynamic & Biomarkers					
28	All Subjects	Non-Standard EFF_L1	Listing of Individual of IL-18		IA1, IA2, SAC
29	All Subjects	Non-Standard EFF_L1	Listing of Individual of NGAL		IA2, SAC
30	All Subjects	Non-Standard EFF_L1	Listing of Individual of KIM1		IA2, SAC
31	All Subjects	Non-Standard PD_L1	Listing of Biomarkers		IA2, SAC
32	All Subjects	Non-Standard PD_L1	Listing of Free and Drug-bound IL-18 Levels In Serum		IA2, SAC
Dialysis dependency and graft survival					
33	All Subjects	Non-Standard SAFE_L1	Listing of Number of Dialysis Events per Patient in the First 30 Days Post Transplant		IA1, IA2, SAC

Non-ICH Listings					
No.	Population	IDSL / TST ID / Example Shell	Title	Programming Notes	Deliverable
Recipient Kidney Data					
34	All Subjects	Non-Standard SAFE_L3	Listing of Recipient Virology		IA2, SAC
Exploratory					
35	All Subjects	Non-Standard SAFE_L1	Listing of Individual % bound GSK1070806 within Renal Graft Biopsies		IA2, SAC
36	All Subjects	Non-Standard SAFE_L1	Listing of Individual Level of IL-18 in Renal Preservation Fluid		IA2, SAC

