11.10. Appendix 10: Example Mock Shells for Data Displays

Example : EFF_F1
Protocol : 204824
Population : All Subjects

Page 1 of X

Figure X
Individual Subject Spaghetti Plot with Mean Line

[figure not shown]

NOTE: This is example only. Plot adjusted accordingly to study data.

Example : EFF_F2
Protocol : 204824
Population : All Subjects

Page 1 of X

Figure X
Individual Subject Spaghetti Plot

[figure not shown]

NOTE: This is example only. Plot adjusted accordingly to study data.

Example : EFF_F3
Protocol : 204824
Population : All Subjects

Page 1 of X

Figure X
Mean Plot of xxx

[figure not shown]

NOTE: Plot adjusted accordingly to study data

Example : EFF_F4
Protocol : 204824
Population : All Subjects

Page 1 of X

Figure X
Kaplan-Meier Curve of Graft Survival up to 12 Months post Transplant

[figure not shown]

NOTE: Plot adjusted accordingly to study data, with plot also including the other treatments groups on subsequent pages.

Example : EFF_F5
 Protocol : 204824
 Population : Safety

Page 1 of X

Figure X
 Patient Profile Plot

[figure not shown]
NOTE: Plot adjusted accordingly to study data, with plot also including the other treatments group and parameters on subsequent pages.

Example : PKPD_F1
 Protocol : 204824
 Population : All Subjects

Page 1 of X

Figure X

Scatter Plot of Free and Drug Bound IL-18 Serum Levels Versus GSK1070806 Plasma Concentration

Treatment

0.008 mg/kg HV +	0.05 mg/kg HV ✕	0.25 mg/kg HV △	1.0 mg/kg HV □	3.0 mg/kg HV *	10.0 mg/kg HV ◊
------------------	-----------------	-----------------	----------------	----------------	-----------------

Note: IL-18 Serum values defined as BLQ, are imputed as half of LLQ.

Note: Analysis numeric results in std units (NQ values not imputed with 0) are considered as Plasma Concentration values.

Note: Free IL-18 plot is not presented as majority of data is BLQ.

Note: Doses = 0.008, 0.05, 0.25, 1.0, 3.0 & 10 mg/kg HV

Example : EFF_T1
 Protocol : 204824
 Population : All Subjects

Page 1 of X

Table X
 Summary Statistics of XXX (unit)

Summary: Absolute

Treatment	N	Visit	Planned Relevant Time	n	Mean	S.D	Median	Min	Max
GSK1070806 3 mg/kg	xx	xx	x		XXX.X	XX.XX	XXX.X	XXX	XXX
	xx		x		XXX.X	XX.XX	XXX.X	XXX	XXX
	xx	xx	x		XXX.X	XX.XX	XXX.X	XXX	XXX
	xx		x		XXX.X	XX.XX	XXX.X	XXX	XXX

Example : EFF_T2
 Protocol : 204824
 Population : All Subjects

Page 1 of X

Table X
 Summary Statistics of XXX (unit)

Summary: Change from Baseline

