Treatment	N	Visit	Planned Relevant Time	n	Mean	S.D	Median	Min	Max
GSK1070806 3 mg/kg	xx	xx	x		XXX.X	XX.XX	XXX.X	XXX	XXX
	xx		x		XXX.X	XX.XX	XXX.X	XXX	XXX
	xx	xx	x		XXX.X	XX.XX	XXX.X	XXX	XXX
	xx		x		XXX.X	XX.XX	XXX.X	XXX	XXX

Example : EFF_T3
Protocol : 204824
Population : All Subjects.

Page 1 of n

Table X
Proportion of Subjects with DGF

	Number of Subjects (%) (N)
Subjects with DGF	XXX (%)

Example : EFF_T4
Protocol : 204824
Population : All Subjects.

Page 1 of n

Table X
Proportion of Subjects with Renal Functional Graft within 7 Days after Transplant

	Number of Subjects (%) (N)
Primary Non DGF	XXX (%)
3 day Functional DGF	XXX (%)
7 day Functional DGF	XXX (%)
3 day Intermediate Graft Function	XXX (%)
7 day Intermediate Graft Function	XXX (%)
3 day Immediate Graft Function	XXX (%)
7 day Immediate Graft Function	XXX (%)

Example : EFF_T5
 Protocol : 204824
 Population : All Subjects

Page 1 of X

Table X
 Summary of Maximum Emergent QTc Values by Category

Baseline (N = xx)				Enhanced Monitoring (N = xx)			
Criteria	N	Mean QTc	SD	Criteria	N	Mean max QTc	SD
QT <= 480 msec	xx	xx.x	xx.xx	QTc > 530 msec	xx	xx.x	xx.xx
				QT (uncorr) > 600 msec	xx	xx.x	xx.xx
Bundle Branch Block with QT <= 500 msec	xx	xx.x	xx.xx	QTc >= 550 msec	xx	xx.x	xx.xx
				QT (uncorr) > 600 msec	xx	xx.x	xx.xx

Note: QTc value could be QTcB or QTcF depends on collected data.

Example : SAFE_L1
 Protocol : 204824
 Population : All Subjects

Page 1 of X

Listing X
Listing of XXX

Treatment	Subj.	Analyte (units)	Visit	Actual Date	Planned Relative Time	Time Sample Taken	Result	Change from Baseline
GSK1070806 3mg/kg	PPD	XXX	DAY 1	PPD	PRE DOSE	9:48	0.9	
			DAY 1		4 Hr	9:48	1.10	0.20
			DAY 29		4 Hr	9:48	2.60	1.70
			DAY 85		4 Hr	9:48	1.10	0.20

NOTE: Table adjusted accordingly to the study data.

Example : SAFE_L2
Protocol : 204824
Population : All Subjects

Page 1 of X

Listing X
Listing of Patients Hospitalization and Re-hospitalization Stay

Subject	Age/Gender	Race	DGF (Y/N)	Hosp. Date	Discharge Date	Length of Stay (Day)
XXXXXXX	XX/X	XX	X	XX/XX/XXXX	XX/XX/XXXX	XX
				XX/XX/XXXX	XX/XX/XXXX	XX
XXXXXXX	XX/X	XX	X	XX/XX/XXXX	XX/XX/XXXX	XX

Example : SAFE_L3
Protocol : 204824
Population : All Subjects

Page 1 of X

Table X
Listing of Donor Virology

Subject	Age/Gender	Race	Virology Type	Positive (yes/no)
XXXXXXX	XX/X	XX	Hepatitis B	
			Hepatitis C	
			HIV	
			EBV	

CONFIDENTIAL

204824

Example : SAFE_L4
Protocol : 204824
Population : All Subjects

Page 1 of X

Table X

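### No planned display links preservation-fluid IL-18 to graft function, and Tables 2.25–2.27 cite a change-from-baseline shell for single-sample measures

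*SAP*

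**What the plan says.** SAP section 2.2 lists the exploratory objective "To assess the relation between IL-18 levels in renal preservation fluid and graft function" and pairs it with one endpoint, "Level of IL-18 in renal preservation fluid". The synopsis in section 1 presents the plan as covering every analysis and output needed for the final study report.

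Table 3 (section 8.1.1) marks two outputs for this endpoint, a summary table and an individual listing, both under Absolute. It marks no figure and nothing under Change from Baseline. The two rows for drug within renal graft biopsies (% free and % bound) are marked the same way.

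The display lists turn these into:

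- Table 2.27, "Summary Statistics of Level of IL-18 in Renal Preservation Fluid" (section 11.9.4), shell EFF_T2, no programming note.
- Tables 2.25 and 2.26 for the biopsy measures, also shell EFF_T2.
- Listing 36, "Listing of Individual Level of IL-18 in Renal Preservation Fluid" (section 11.9.11), shell SAFE_L1.

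In section 11.10, shell EFF_T2 is headed "Summary: Change from Baseline" and shell EFF_T1 is headed "Summary: Absolute". Baseline is the latest pre-dose assessment (section 11.4.1.1). Section 11.4.1.2 adds that "if baseline data is missing no derivation will be performed and will be set to missing".

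**The concern.** There are two separate faults.

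The first is one of substance. The objective asks about a relation between two variables, but the plan summarises only one of them. An overall mean and standard deviation of fluid IL-18, correctly laid out, say nothing about whether the level differs between grafts that function at once and grafts that do not.

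The second is one of specification. Three tables point to a layout that reports change from baseline for measures taken once.

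At stake is whether this exploratory question is addressed by a comparison fixed in advance or by one chosen after the data have been seen.

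**Working it through.** The plan attaches no figure to this objective, so the check is a trace from objective to output, followed by the size of the comparison that could be made.

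**Step 1: does any output cross fluid IL-18 with graft function?**

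| Place in the SAP | Fluid IL-18 shown | Graft function shown |
|---|---|---|
| Table 2.27 | Yes, overall summary | No |
| Listing 36 (shell SAFE_L1) | Yes, by subject | No |
| Tables 2.01, 2.02 and 2.08 | No | Yes |
| Listing 25 | No | Yes, by subject |
| Section 9.1, Figure 5.01, Listing 41 | No (serum IL-18 against drug concentration) | No |

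No output shows both.

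**Step 2: can a change from baseline be derived for Table 2.27?** The Time and Events table (section 11.2) schedules one fluid sample per subject, taken at back-table preparation. Note 15 lets the infusion run at any point before or during the operation, provided it ends before reperfusion. The sample may therefore fall on either side of dosing:

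- Sample before dosing: it is itself the baseline, and there is no later value.
- Sample after dosing: there is no baseline, and section 11.4.1.2 sets the change to missing.

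Neither case gives a change value.

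**Step 3: and for Tables 2.25 and 2.26?** The scheduled study biopsy is post-reperfusion, at about 45 minutes, and the infusion must be complete before reperfusion. The biopsy is always post-dose, so no baseline exists and the change is missing.

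**Step 4: which reading does the rest of the plan support?** Table 3 marks all three measures as absolute only, and none of the three titles mentions change. For the serum biomarkers (Tables 2.11–2.20), EFF_T1 goes with the absolute tables and EFF_T2 with those titled as change from baseline. EFF_T2 on Tables 2.25–2.27 is therefore at odds with the plan's own usage.

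**Step 5: how large would a split by DGF status be?** Inputs are the maximum sample size of 30 and the two DGF rates in the section 1 synopsis, 35% and 50%. Assume all 30 are enrolled and sampled.

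- At 35%: 0.35 × 30 = 10.5 with DGF and 30 − 10.5 = 19.5 without.
- At 50%: 0.50 × 30 = 15 with DGF and 15 without.

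That is roughly 10–15 versus 15–20 subjects. Early stopping shrinks this. In Figure 1, at 6 subjects only 0 events (0.936, above 92%) or 6 events (0.009, below 2%) crosses a boundary. A stop at that look would leave one group empty.

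**The case against.** A reader might infer that the planned output is empty, or that the trial cannot answer its own question. The document does not support either reading.

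- Table 2.27 is not the only output. Table 3 plans an absolute summary and an absolute listing, and Listing 36 reports each subject's level whatever happens to the table.
- Table 2.27 comes out blank only if one shell code is followed literally against the table's own title and Table 3. EFF_T1 and EFF_T2 have the same columns and differ only in their label, and the appendix offers its shells as examples. EFF_T2 is also assigned to Table 2.10 (rejection episodes), where change makes no sense. This looks like loose coding that a programmer would probably query, not a decision to analyse change.
- Listing 36 and Listing 25 both cover All Subjects and are both delivered at IA2 and SAC. With at most 30 subjects they could be matched by hand.
- Listing shell SAFE_L1 carries the remark "NOTE: Table adjusted accordingly to the study data", so some adaptation is foreseen.

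All of this stands, and it limits the point. It does not remove it. Matching two listings by hand is possible but is planned nowhere. The remark on adaptation belongs to SAFE_L1; EFF_T2 carries none. Listings 23 and 24 are expressly told to omit the change column, and Listing 36 is not. Correcting the shell alone would still leave an overall summary that cannot address a relation.

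**Conclusion.** The point holds in two limited parts. First, no planned output relates preservation-fluid IL-18 to graft function, although section 2.2 makes that relation an objective. This is true whichever shell is used. Second, Tables 2.25–2.27 cite a change-from-baseline shell for single-sample measures that Table 3 plans as absolute, and no change can be derived for any of them.

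The consequence is small. The objective is exploratory, the primary analysis is untouched and no data are lost. The conclusion rests on the schedule in section 11.2 and the display lists being complete, as the synopsis claims. The group sizes rest on full enrolment, a usable fluid sample from every subject and a DGF rate between 35% and 50%. They are an upper range and support description only.

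**What to change.** - Assign shell EFF_T1 to Tables 2.25, 2.26 and 2.27.
- Present Table 2.27 by DGF status (yes/no). Show separately any dosed subject without a DGF classification, since the table is on All Subjects.
- Add DGF status to Listing 36 and a programming note dropping its change-from-baseline column, as already done for Listings 23 and 24.
- A further split by 7-day graft-function category is optional, because the groups may be very small.

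If the sponsor does not want the comparison, the alternative is to reword the objective as a description of the fluid level.

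The cost is three shell references, one by-group column and one listing note, with no new data. Shell SAFE_L2 already has a DGF column that can be copied. The change should be made before database freeze so that the comparison is not chosen after results are known.

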2.3. Study Design

Overview of Study Design and Key Features	

The diagram illustrates the study timeline. It starts with a 'Screening' phase, followed by an 'Inpatient' phase where a 'Single dose' of 'all-18mAb' is administered. This is followed by an 'Outpatient follow-up' phase. A green arrow points to the 'all-18mAb Single dose' point. Below the timeline, a purple bar represents 'Standard transplant immunosuppression' which begins during the inpatient phase and continues through the outpatient follow-up. The timeline is marked with time points: 12h, 0d (Primary endpoint), 7d, 30d, 90d, 6m, and 12m.
	
Overview of Key Study Design Features	
Design Features :	
 Multi-centre, single arm Bayesian sequential design.
Dosing :	
 A single infusion prior to kidney allograft reperfusion.
Treatment Assignment :	
 Single arm study. All patients will be received GSK1070806. No randomization is needed.
Interim Analysis	
 DGF data will be reviewed sequentially. Safety, tolerability and efficacy data will be reviewed by the GSK study team on an ongoing basis throughout the study. An interim analysis will be performed after recruitment of 8 to 10 patients to review for a consideration of dose adjustment based on an integrated review of safety/tolerability, efficacy, and exposure. Once the last patient completes 7-Days post-transplant, an interim analysis will be performed of all available data for the primary endpoint in addition to supportive efficacy and safety data. The results of this interim analysis will be reviewed by the GSK study team and other relevant GSK staff for internal decision making.

